# 6. Randomization and blinding

#### 6.1.1 Randomization

Eligible patients will be randomized in a 1:1 ratio to either cenegermin ophthalmic solution 20 mcg/mL TID or vehicle ophthalmic solution TID.

Randomization will be stratified by site to ensure balanced assignment across treatment groups. The stratified permuted block randomization list will be generated with a computer procedure by an independent statistician not involved in the conduct of the study.

Randomization will be performed through IRS. Each Patient Kit number will be randomly associated with a treatment group. The randomization list will be provided to the facility responsible for IMP packaging/labelling for the purpose of IMP preparation. Each randomized patient will be allocated with randomization number according to the stratified randomization list. Dropouts after randomization will not be replaced.

The enrollment of patients will be scheduled in order to assure an inclusion of approximately 80 patients to ensure at least 72 patients assuming up to 10% of patients not evaluable after enrollment.

# 6.1.2 Unblinding

The identity of the treatments will remain unknown to the patient, investigator, site staff and Sponsor's clinical research personnel until the completion of the study (after full data base lock) except in case of specific events that will require unmasking of the patient.

The vials containing cenegermin (20 mcg/mL) or vehicle will be identical in appearance, and the contents of the vials will be indistinguishable. All staff directly involved in the analysis of study results will remain masked to treatment assignments while the study is in progress.

The investigator will be provided with a protected access to the randomization list so only in case of a medical emergency the investigator can open the treatment allocation for a specific patient.

Also Dompé's Pharmacovigilance contact person will be provided with a protected access to randomization list, so if required by the Pharmacovigilance activities the Pharmacovigilance contact person can open the treatment allocation for a specific Patient.

In the event of a medical emergency where the knowledge of patient treatment is required to provide the patient with appropriate care, investigators will have the possibility to unmask the treatment assignment for a specific patient. The investigators are encouraged to contact the Contract Research Organization staff before becoming unmasked if there is sufficient time.

If the investigator becomes unmasked for any reason, this information will be recorded on source data and in the eCRF of the study, specifying the date and the reason.

Unmasking events will be recorded and reported in the final study report.

### 6.2 Overview of planned statistical analyses

Analyses will be conducted when all enrolled subjects have completed the study and the study database has been locked and unblinded. Key first efficacy results (KFR) will be provided close to the database closure in order to identify efficacy findings in a short timeframe.

The list of tables, listings, and figures to be provided at each analysis is reported in appendix 15.

### 7. Statistical Analysis

### 7.1 General

All patient data collected during the study will be listed by patient and site.

Appropriate descriptive statistics will be produced by treatment arms according to the nature of the variable.

For continuous data, number of observations, mean, standard deviation, median, Q1-Q3, range (minimum and maximum) and 95% confidence intervals will be presented.

For categorical data, frequency distributions and percentages with 95% confidence intervals (Wilson method) per category will be presented.

For primary analysis, the threshold for claiming statistical significance will 0.025 one-sided. For other analysis, unless otherwise specified, the significance level for statistical testing will be 0.05 and two-sided tests.

The statistical analyses (both descriptive and inferential) of some endpoints will be done on the eligible eye when applicable. Details will be provided in the statistical analysis outputs as notes.

Additional post-hoc analysis may be produced to further allow comparison between treatment and control, according to the results obtained. Any deviations from the original statistical plan (including unplanned analyses) will be documented in the CSR.

#### 7.2 Analysis sets

#### 7.2.1 Screened set

The Screened set will consist of all patients with signed written informed consent.

# 7.2.2 Enrolled set (ENR)

The ENR set will consist of all patients with signed written informed consent and fulfillment of eligibility criteria (i.e., not reported as screening failure).

7.2.3 Randomized set (RND)

The RND set will consist of all patients in the ENR set who are randomized to the study, regardless of whether they receive the IMP or not.

7.2.4 Full Analysis set (FAS)

The FAS population will consist of all randomized patients who received at least one dose of the investigational product. FAS population will be analyzed according to intention-to-treat (ITT) principle, i.e. by treatment allocation regardless happening of intercurrent events (treatment policy strategy). The FAS population will be used for the primary analysis of the study and to present results on efficacy data.

7.2.5 Safety set (SAF)

The SAF set will consist of all randomized patients who received at least one dose of the investigational product. SAF set will be analyzed according to the actual treatment received. The SAF population will be used to present results on safety data.

7.2.6 Per Protocol set (PP)

The PP set will consist of all randomized patients who received at least one dose of the investigational product and do not have Major Protocol Deviations. The PP population will be used for sensitivity analyses.

# 7.3 Primary estimand

The primary endpoints will be analyzed using treatment policy estimands, defined by the following:

Primary endpoint:

- Population: Adult patients with severe Sjogren's dry eye disease under treatment with Cyclosporine A, as defined by the inclusion-exclusion criteria of the study (and matching the FAS definition);
- Variable: Schirmer I test at week 4;
- Intercurrent event: The occurrence of an intercurrent event is irrelevant. All observed values will be used regardless of occurrence of an intercurrent event. Retrieved drop-outs will be used for data imputation of missing data;
- Population-level summary: Difference in proportion of patients reaching a value of Schirmer I test (without anesthesia) >10mm/5min at week 4.

Coprimary endpoint:

- Population: Adult patients with severe Sjogren's dry eye disease under treatment with Cyclosporine A, as defined by the inclusion-exclusion criteria of the study (and matching the FAS definition);
- Variable: SANDE global score at week 12;

- Intercurrent event: The occurrence of an intercurrent event is irrelevant. All observed values will be used regardless of occurrence of an intercurrent event. Retrieved drop-outs will be used for data imputation of missing data;
- Population-level summary: Difference in means of change from baseline in the global SANDE score at week 12.

# 7.4 Usage of analysis sets

The usage of the analysis sets for the creation of tables and figures is illustrated in Table 2. Unless otherwise specified, all listings will be done for RND set. All listings will report:

- planned and actual treatment names included,
- the flag(s) of the analysis set(s) used to analyze the information of the listing (according to Table 2).

| Analysis   | ENR | RND | FAS | SAF | PP |
|--|-----|-----|-----|-----|----|
| Subject enrolment and disposition                            | Х   |     |     |     |    |
| Protocol deviations  |     | Х   |     |     |    |
| Study discontinuations                                       |     | Х   |     |     |    |
| Demographics and baseline characteristics                    |     |     | Х   |     |    |
| Ocular and systemic Medical History and Concomitant Diseases |     |     | Х   |     |    |
| Prior and concomitant medications                            |     |     | Х   | Х   |    |
| Dry Eye History  |     |     | Х   |     |    |
| Other baseline characteristics                               |     |     | Х   |     |    |
| Evaluation of Treatment Compliance and Exposure              |     |     | Х   | Х   |    |
| Evaluation of Efficacy                                       |     |     | Х   |     |    |
| Analysis of primary efficacy endpoint                        |     |     | Х   |     |    |
| Sensitivity analyses   |     |     | Х   |     |    |
| Supportive analyses  |     |     | Х   |     | Х  |
| Analysis of secondary efficacy endpoints                     |     |     | Х   |     |    |
| Evaluation of Safety   |     |     |     | Х   |    |

Table 2: Usage of analysis set

#### 7.5 Sub-group analyses

Subgroup analyses of primary and secondary endpoints will be performed on the following subgroups of baseline characteristics:

- Age class (*Median*, *Median*).
- Race.
- Ethnicity.
- Gender.

Within each subgroup level, descriptive in nature analyses will be performed on:

- Schirmer I test.
- SANDE global, frequency and severity scores.
- NEI scale.

- TFBUT.
- IDEEL questionnaire.

at each available timepoints by means of descriptive statistics.

In case of continuous measures, analyses will be provided for baseline visit, each post-baseline visit, and their change from baseline. Comparisons between treatments will be performed using twosample t-test (assuming unequal variances) or, if the required assumptions are not met, the twosample Mann–Whitney U test will be used. Assumption of normal distribution of endpoints for continuous data will be assessed by a visual inspection of distribution.

In case of categorical variables, the Fisher's Exact test will be provided in addition to summary description.

Statistical tests for interaction (between subgroup variable and treatment arm) will be performed before investigating further subgroups: analyses of primary endpoints will be performed using regression models including treatment, subgroup variable and their interaction as covariate. If the interaction between subgroup variable and treatment arm is statistically significant at 15% nominal level in at least one regression model, then subgroup analysis will be performed.

Variables that may be evaluated after test for interaction are:

- Region (Europe, US),
- Sjögren's syndrome (primary, secondary), where "primary" is defined as a confirmed diagnosis of Sjögren's syndrome while "secondary" as other autoimmune disease known to induce Sjögren's Dry Eye Disease,
- Medical history,
- Concomitant medication.

Subgroup levels may be pooled to have an adequate number of subjects per strata to perform the analysis. Decision on pooling will be taken during the Blind Data Review Meeting (BDRM) before data base lock.

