## 9.4.6. Subgroup analysis

Subgroup analyses of primary and secondary endpoints will be performed on the following subgroups of baseline characteristics:

- Age class (*Median*, *Median*),
- Race,
- Gender,
- Ethnicity,
- Sjögren's syndrome (primary, secondary).

Statistical details and potential new subgroups definitions will be reported in the SAP.

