| Table 14.2.6.2.4 Subgroup evaluation: Change from baseline in the global SANDE score at week 12 - Analysis of Covariance (ANCOVA) -         Treatment by concomitant medication interaction- Multiple imputation. Full analysis set |     | x              |
| Table 14.2.6.3.1 Absolute values and change from baseline in Schirmer I test at each timepoint by age class. Full analysis set  |     | x              |

| Number - Title - Population   | KFR | Final analysis |
|---|-----|----------------|
| Table 14.2.6.4.1 Absolute values and change from baseline in Cornea and conjunctiva vital staining with fluorescein (NEI scale) at each                               |     | x              |
| timepoint by age class. Full analysis set   |     | ^              |
| Table 14.2.6.5.1 Absolute values and change from baseline in TFBUT at each timepoint by age class. Full analysis set  |     | x              |
| Table 14.2.6.6.1.1 Absolute values and change from baseline in SANDE global scores at each timepoint by age class. Full analysis set                                  |     | x              |
| Table 14.2.6.6.2.1 Absolute values and change from baseline in SANDE severity scores at each timepoint by age class. Full analysis set                                |     | x              |
| Table 14.2.6.6.3.1 Absolute values and change from baseline in SANDE frequency scores at each timepoint by age class. Full analysis set                               |     | x              |
| Table 14.2.6.7.1.1 Absolute values and change from baseline in IDEEL Quality of Life module at each timepoint by age class. Full analysis set                         |     | x              |
| Table 14.2.6.7.2.1 Absolute values and change from baseline in IDEEL Dry eye Treatment satisfaction & Bother module at each timepoint by age class. Full analysis set |     | x              |
| Table 14.2.6.7.3.1 Absolute values and change from baseline in IDEEL Dry eye Symptom bother module at each timepoint by age class. Full analysis set                  |     | x              |
| Table 14.2.6.y.x Repeated set of tables form 14.2.6.3.1 to 14.2.6.2.7.3.1 for all subgroups   |     | x              |
| Table 14.3.1.1 Summary of treatment emergent adverse events (TEAE). Safety set  |     | x              |
| Table 14.3.1.2 Summary of Ophthalmic TEAEs by primary SOC and PT by study periods. Safety set   |     | x              |

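### The four always-run subgroups get within-level p-values but no interaction test, and the by-level results for Sjögren's type that the protocol promised are made conditional without being logged as a change

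*SAP*

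**What the plan says.** **Always-run subgroups.** SAP 7.5 names age class, race, ethnicity and gender as subgroups for the primary and secondary endpoints. It then states: "Within each subgroup level, descriptive in nature analyses will be performed on" a list of measures (Schirmer I, the three SANDE scores, NEI, TFBUT, IDEEL). For continuous measures, "Comparisons between treatments will be performed using twosample t-test (assuming unequal variances"), with Mann–Whitney as the fallback. For the rest, "In case of categorical variables, the Fisher's Exact test will be provided in addition to summary description". No treatment-by-subgroup model is planned for these four factors.

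**Gated subgroups.** The same section says "Statistical tests for interaction (between subgroup variable and treatment arm) will be performed before investigating further subgroups". The models are those of the co-primary endpoints with a treatment-by-subgroup term, and subgroup analysis follows if the interaction reaches the 15% nominal level in at least one of them. "Variables that may be evaluated after test for interaction are" region, Sjögren's type, medical history and concomitant medication.

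**Protocol.** Section 9.4.6 says: "Subgroup analyses of primary and secondary endpoints will be performed on the following subgroups of baseline characteristics". Its list is age class, race, gender, ethnicity and Sjögren's type (primary, secondary), with no condition on any of them. It leaves statistical details and possible new subgroups to the SAP.

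**Change log.** SAP 7.9 itemises departures from the protocol. The conditional status of Sjögren's type is not among them.

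**Tables (SAP 15.1).** The interaction tables 14.2.6.1.1–4 (Schirmer I responder, week 4) and 14.2.6.2.1–4 (SANDE, week 12) cover only the four gated variables. The by-level tables start at 14.2.6.3.1, "Absolute values and change from baseline in Schirmer I test at each timepoint by age class", and continue with NEI, TFBUT, SANDE and IDEEL. None shows the >10 mm/5min responder endpoint.

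**The concern.** A subgroup section is there to answer whether the treatment effect is consistent across types of patient. A test inside each level answers something else: whether that level, alone and with part of the sample, reaches p<0.05. With 72 evaluable patients split in two, a significant result in one half and a non-significant one in the other is a common outcome even when the effects are equal. The SAP recognises the better tool, since it specifies interaction models for its second-tier variables, but it does not apply it to the factors it always reports.

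The second issue is a protocol commitment. The trial enrols patients with Sjögren's syndrome and patients with other autoimmune disease causing Sjögren's dry eye. Whether both groups benefit is a natural question, and the protocol undertook to report it. Under the SAP, the by-level results, including every secondary endpoint, appear only if a screening test happens to pass. A finding of consistency is what the screen is most likely to suppress.

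**Working it through.** **Inputs.** From SAP section 5: 72 evaluable patients, 1:1, so 36 per arm; SANDE difference 10, SD 12; Schirmer I responders 33% on vehicle and 75% on cenegermin (33% + 42%); one-sided alpha 0.025. From SAP 7.1 for subgroup tests: "For other analysis, unless otherwise specified, the significance level for statistical testing will be 0.05 and two-sided tests". From SAP 7.5: 15% gate, at least one of two co-primary models. Assumed, because the documents do not give it: the split of patients between levels. The age split is by median, so equal halves are close to what the plan implies there.

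**Step 1. The plan's own power figures.** Two-proportion normal approximation (pooled variance under the null), 36 per arm, 0.33 v 0.75: 96.3%, as stated. Two means, normal approximation, 36 per arm, 10/12: 94.2% against the stated 94.1% (noncentral t gives 93.7%). Product of the stated powers: 0.963 × 0.941 = 0.906, consistent with the stated 90%. The inputs are sound to build on.

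**Step 2. Within-level tests when the effect is the same in both halves.** Each age half has 18 per arm. Noncentrality = 10 / (12 × √(2/18)) = 10/4 = 2.5 on 34 df; two-sided 5% critical value 2.03; power = 0.680. The halves are independent, so P(exactly one significant) = 2 × 0.680 × 0.320 = 0.435. With unequal levels:

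| Split | Power, larger level | Power, smaller level | P(exactly one significant) |
|---|---|---|---|
| 50:50 | 0.680 | 0.680 | 0.435 |
| 70:30 | 0.826 | 0.453 | 0.531 |
| 85:15 | 0.894 | 0.231 | 0.712 |

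The apparent contrast becomes more likely as the split becomes more uneven, with no true difference at all.

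**Step 3. The Sjögren's gate with no interaction.** Each model passes with probability 0.15. If the two tests are independent, both fail with probability 0.85² = 0.7225, so by-level results are omitted about 72% of the time. With a correlation of 0.3 to 0.5 between the tests, the simulated chance that the gate opens is 27% to 26%, so the answer barely moves.

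**Step 4. The gate with a real SANDE interaction (10 in one type, 0 in the other) and none on Schirmer I.** SE of the interaction = 12 × √(2/(36f) + 2/(36(1−f))), where f is the share of patients in one type; the two-sided 15% critical value is 1.44.

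- f = 0.5: SE = 12 × √(2/18 + 2/18) = 5.66; 10/5.66 = 1.77; the SANDE test passes with probability 0.629. Omitted = (1 − 0.629) × 0.85 = 0.315.
- f = 0.8: SE = 12 × √(2/28.8 + 2/7.2) = 7.07; 10/7.07 = 1.41; the test passes with probability 0.492. Omitted = (1 − 0.492) × 0.85 = 0.432.

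The factor 0.85 is the chance that the Schirmer I model does not open the gate by itself.

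**Step 5. What an interaction test can deliver.** At two-sided 5% with equal halves, power for a 10-point SANDE interaction = P(Z > 1.96 − 1.77) ≈ 0.42. The 95% CI half-width is 1.96 × 5.66 = 11.1 points.

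**The case against.** The strongest reply is that the within-level tests are expressly descriptive. They lie outside the co-primary test and outside the key secondary hierarchy, and nothing in the SAP says that a significant result in one level only will be read as a different effect. That stands: no confirmatory claim or type I error rate is at stake. It does not justify the p-values, because a two-arm p-value printed for each level invites the comparison that it cannot support.

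Three stronger readings are tempting, and the documents do not support them.

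- A reader might infer that the report could say nothing about consistency across Sjögren's types. Tables 14.2.6.1.2 and 14.2.6.2.2 fit the treatment-by-Sjögren's interaction for both co-primary endpoints and are listed for the final analysis without condition; they have to be run, since they are the gate. What can be lost is the by-level results.
- A reader might infer that the responder endpoint is absent from the subgroup work altogether. It is the subject of Tables 14.2.6.1.1–4. It is missing only from the by-level tables, although SAP 7.5 covers primary endpoints and provides Fisher's exact test for categorical variables.
- A reader might judge the gate on the SANDE model alone (63% and 49% detection in step 4). Either model can open it, so the figures are 1 − 0.315 = 68.5% and 1 − 0.432 = 56.8%.

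One could also count 9 measures × 5 post-baseline visits × 8 levels = 360 within-level tests, with about 18 below 0.05 by chance. That needs two levels each for race and ethnicity, which the documents do not state and blind-review pooling could change, and no effect on any measure at any visit. The conclusion does not rest on it.

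Finally, interaction tests in 72 patients are weak (step 5). That is fair, and it argues for estimates with intervals rather than for a different set of p-values.

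**Conclusion.** The point holds, as a matter of exploratory analysis and reporting. For age class, race, ethnicity and gender, the plan produces p-values that cannot address whether effects differ; under the planning assumptions and a homogeneous effect, about 43% of trials would show one age half significant on SANDE at week 12 and the other not. For Sjögren's type, the SAP makes conditional an analysis that the protocol states without condition, and SAP 7.9 does not say so. The protocol's delegation of details and new subgroups to the SAP does not extend to making a listed subgroup optional. By-level results would be omitted about 72% of the time with no interaction, and about 32% (equal split) to 43% (80/20) with a 10-point SANDE interaction.

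These figures assume the SAP's SANDE effect and SD, 72 evaluable patients and unadjusted comparisons. The gate figures also assume independent tests, and the last two further assume no Schirmer I interaction and the stated splits. The primary conclusions of the trial are untouched.

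**What to change.** In SAP 7.5 and 15.1:

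1. Extend the existing co-primary interaction models to age class, race, ethnicity and gender.
2. Report the by-level results for Sjögren's type unconditionally, as the protocol states. If the sponsor prefers the gate, record it in SAP 7.9 as a change, with the reason.
3. Replace within-level p-values by the treatment effect in each level, and the interaction estimate, each with a 95% CI.
4. Add the >10 mm/5min responder endpoint to the by-level tables.

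The cost is some SAP wording and a few more exploratory tables. The models are already specified for other variables, and small levels can be pooled at the blind data review, as SAP 7.5 allows. No data collection or primary analysis changes. The added interaction tests will have low power, so the text should direct readers to the estimates and intervals and state that a non-significant interaction does not establish consistency.

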# 5. Sample size justification

The sample size of the study is calculated based on results from previous studies.

Sample size was calculated according to the following assumptions:

- randomization ratio 1:1.
- a difference of 42% in Schirmer I rate of responders (value >10mm/5min at week 4.) in favor of rhNGF treatment at Week 4, with a responder rate of 33% for vehicle.
- 10 points in Global SANDE score improvement at Week 12, with a standard deviation of 12 points.

Based on these assumptions, a total sample size of 72 evaluable patients (80 pts considering 10% of patients not evaluable after enrollment) allows to achieve an overall power of 90% to show superiority of rhNGF eye drops solution vs vehicle in terms of primary endpoint, considering a one-sided alpha of 0.025.

Specifically:

- A power of 96.3% is achieved for Schirmer I primary endpoint.
- A power of 94.1% is achieved for SANDE primary endpoint.

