If there are not enough retrieved dropouts for convergence of MI-RD regression model, a referencebased Multiple Imputation (MI) approach will be adopted to consider a missing not at random (MNAR) mechanism for missing data: imputation of values in the rhNGF arm (above step #2) will be done using the non-missing values from the control group (this approach will be referred as "Copy Reference"). This approach does not assume benefits for rhNGF in case of discontinuation and limits a post-discontinuation clinical effect to that of vehicle. The final decision on the use of the MI-RD vs Copy-Reference for this endpoint will be done at the time of the analysis and reported in the CSR.

Whether for MI-RD or Copy-Reference approach, the adjusted estimated treatment differences in proportions between cenegermin and vehicle at week 4 will be displayed together with the corresponding two-side 95% confidence intervals and p-value.

### 10.1.2.2 Change from baseline in the global SANDE score at week 12

This co-primary endpoint will be analyzed by means of an Analysis of Covariance (ANCOVA) adjusting by pre-defined baseline factors (gender, age class, baseline global SANDE score as fixed effects and site as random effect) and a one-sided test will be used to test for differences between treatment groups. Rules for derivation of SANDE scores are reported in section 12.2.

For the imputation of missing data, a regression model will be created by including the baseline global SANDE score, gender, age class, and intermediate global SANDE scores up to week 12. Two hundred data sets will be generated, and the random seed number will be 252404. MI will be implemented in the following steps:

- 1. Partial imputation assuming MAR will be carried out to impute intermittent (non-monotone) missing data of global SANDE score based on a multivariate joint Gaussian imputation model using the MCMC method. A separate imputation model will be used for each treatment arm. In case of non-convergence or non-estimability issues, a single imputation model will be considered (with treatment arm added as explanatory variable to the model). A total of 200 datasets will be created. These datasets will be utilized in Step #2.
- 2. The remaining monotone missing data will be imputed using a MI regression including the same explanatory variables of the previous step. According to MI-RD approach, only non-missing values from retrieve dropouts will be used to inform the regression model.

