| Table 14.2.5.4.2 Absolute values and change from baseline in IDEEL Dry eye Treatment satisfaction & Bother module at each timepoint. Full analysis set  | x   | x              |
| Table 14.2.5.4.3 Absolute values and change from baseline in IDEEL Dry eye Symptom bother module at each timepoint. Full analysis set   | х   | x              |
| Table 14.2.5.5 Absolute values and change from baseline in Cornea and conjunctiva vital staining with fluorescein (NEI scale) at each timepoint. Full analysis set  | x   | x              |
| Table 14.2.5.6 Absolute values and change from baseline in TFBUT at each timepoint. Full analysis set   | х   | x              |
| Table 14.2.6.1.1 Subgroup evaluation: Schirmer I test (without anesthesia) >10mm/5min at week 4 - Treatment by region interaction- Logistic regression model - Multiple imputation. Full analysis set                               |     | x              |
| Table 14.2.6.1.2 Subgroup evaluation: Schirmer I test (without anesthesia) >10mm/5min at week 4 - Treatment by Sjögren's syndrome interaction- Logistic regression model - Multiple imputation. Full analysis set                   |     | x              |
| Table 14.2.6.1.3 Subgroup evaluation: Schirmer I test (without anesthesia) >10mm/5min at week 4 - Treatment by medical history interaction-
Logistic regression model - Multiple imputation. Full analysis set                   |     | x              |
| Table 14.2.6.1.4 Subgroup evaluation: Schirmer I test (without anesthesia) >10mm/5min at week 4 - Treatment by concomitant medication interaction- Logistic regression model - Multiple imputation. Full analysis set               |     | x              |
| Table 14.2.6.2.1 Subgroup evaluation: Change from baseline in the global SANDE score at week 12 - Analysis of Covariance (ANCOVA) -
Treatment by region interaction- Multiple imputation. Full analysis set                      |     | x              |
| Table 14.2.6.2.2 Subgroup evaluation: Change from baseline in the global SANDE score at week 12 - Analysis of Covariance (ANCOVA) - Treatment by Sjögren's syndrome interaction- Multiple imputation. Full analysis set             |     | x              |
| Table 14.2.6.2.3 Subgroup evaluation: Change from baseline in the global SANDE score at week 12 - Analysis of Covariance (ANCOVA) -
Treatment by medical history interaction- Multiple imputation. Full analysis set             |     | x              |

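### SAP 7.5 lists only treatment, subgroup and their interaction for the exploratory interaction models and does not carry over the covariates of the co-primary models

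*SAP*

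**What the plan says.** SAP 7.5 names four variables that may be examined after an interaction test: region, Sjögren's type, medical history and concomitant medication. For that test, "analyses of primary endpoints will be performed using regression models including treatment, subgroup variable and their interaction as covariate". If the interaction reaches a nominal 15% level in at least one of the two co-primary models, the subgroup analysis is run. The section does not refer to SAP 10.1.2, and Appendix 15.4 gives code for the two primary analyses only.

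The co-primary models contain more terms. SAP 10.1.2.2 specifies the SANDE ANCOVA as "adjusting by pre-defined baseline factors (gender, age class, baseline global SANDE score as fixed effects and site as random effect"). SAP 10.1.2.1 gives the Schirmer logistic model the same structure, with baseline Schirmer I. Site is also the randomisation stratum (SAP 6.1.1).

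SAP 15.1 lists eight interaction tables, four per co-primary. Tables 14.2.6.2.1 to 14.2.6.2.4, for SANDE, are titled ANCOVA. The title of 14.2.6.2.2, for example, ends "Treatment by Sjögren's syndrome interaction- Multiple imputation. Full analysis set". The four Schirmer tables are titled logistic regression, also with multiple imputation.

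**The concern.** Someone programming from SAP 7.5 alone would fit treatment, subgroup and their product. The SANDE interaction would then be tested on an unadjusted change score. Any variation explained by baseline would stay in the residual, and the model would differ from the one whose treatment effect is being explored. A noisier test misses real heterogeneity more often.

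The text also leaves two defensible models, and so two p-values that could fall on either side of 0.15, with nothing in the SAP to choose between them. One gated variable is primary versus secondary Sjögren's syndrome, which Protocol 9.4.6 lists as a planned subgroup without any condition.

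**Working it through.** **1. The plan's own figures.** Inputs from SAP 5: "randomization ratio 1:1", "considering a one-sided alpha of 0.025", "a difference of 42% in Schirmer I rate of responders", "with a responder rate of 33% for vehicle", and "10 points in Global SANDE score improvement at Week 12, with a standard deviation of 12 points"; 72 evaluable patients, so 36 per arm.

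- SANDE: 10 / (12 × √(2/36)) = 10 / 2.828 = 3.536. Power = Φ(3.536 − 1.960) = 94.2%, against 94.1% stated.
- Schirmer, 75% versus 33%, pooled-variance test: 96.3%, as stated.

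Both reproduce. The SAP states no power for any interaction test.

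**2. SANDE interaction test as listed.** Assumptions: SD 12 is the SD of the change score, the subgroups are equal (18 patients per cell), the true interaction is 10 points (for example 15 versus 5), and the 15% level is two-sided.

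- SE = 12 × √(4/18) = 5.66.
- Power from the noncentral t with 68 df and noncentrality 10 / 5.66: 62.4%.

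**3. The same test with baseline added.** If r is the correlation of baseline with change, the residual SD becomes 12 × √(1 − r²), with 67 df. At |r| = 0.5 the SE is 5.66 × √0.75 = 4.90 and power is 72.1%.

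| \|r\| | Gain in power (points) |
|---|---|
| 0.2 | 1.3 |
| 0.3 | 3.1 |
| 0.4 | 5.9 |
| 0.5 | 9.7 |
| 0.6 | 15.0 |
| 0.7 | 22.1 |

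At |r| = 0.5, across 50/50, 30/70 and 20/80 splits, the gain is 3.0 to 4.5 points for a 5-point interaction, 8.5 to 9.7 for 10 points and 6.2 to 9.2 for 15 points.

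**4. What r depends on.** If the baseline and week-12 SDs are equal, r² = (1 − ρ)/2, where ρ is the baseline-to-week-12 correlation. Then ρ of 0.3, 0.5 and 0.7 give gains of 14.5, 9.7 and 5.5 points. Equal SDs are a further assumption, and entry requires a SANDE score above 25, which truncates the baseline spread. At ρ = 0.5 the gain falls to 3.8, 1.7 and 0.4 points if the baseline SD is 0.8, 0.7 and 0.6 of the week-12 SD.

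**5. The gate.** It opens if either model is significant. Take the two tests as independent and |r| = 0.5.

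- No Schirmer interaction (15% pass by chance): 1 − 0.85 × (1 − 0.624) = 68% rises to 1 − 0.85 × (1 − 0.721) = 76%, a gain of about 8 points.
- Schirmer test with 50% power: 81.2% rises to 86.1%, a gain of about 5 points.

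**6. Schirmer.** A simulated logistic interaction test used 72 patients, equal subgroups, vehicle at 33% and about 3,000 replicates per setting. Baseline added about 0 points when not prognostic, 1 to 2 at a log-odds of 0.5 per SD, and about 5 at 1.0 per SD. Entry limits baseline Schirmer I to 2 to 5 mm.

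**7. Site.** The documents give no between-site variance, so no gain can be calculated.

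**The case against.** The strongest reply is that SAP 7.5 introduces its terms with the word including, which is not exhaustive, and says nowhere that covariates are removed. The interaction tables carry the same model labels as the primary tables. A model with treatment, a categorical subgroup and their product has no continuous covariate, so the ANCOVA title suggests the primary model with a term added.

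This stands in part. It rules out saying that the SAP orders the covariates dropped. It does not settle the model. Where the SAP reuses a primary model elsewhere, it says so by cross-reference (10.1.4, 10.2.2.1 to 10.2.2.3). Its term lists also differ between models: the MMRMs of 10.2.2.4 to 10.2.2.6 list gender, age class and baseline but not site. Unlisted terms therefore cannot be assumed to carry over, and the sentence and the table titles still point to different models.

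It is also fair to object that little is at stake. All eight interaction tables are listed for the final analysis whichever way the gate falls. The gate controls only descriptive subgroup analyses, and post-hoc comparisons are allowed if documented (SAP 7.1). No co-primary test, key secondary test or alpha is affected. That stands in full.

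**Conclusion.** SAP 7.5 lists three terms, omits those of 10.1.2 and does not fit its own table titles. Followed literally, it weakens the exploratory SANDE interaction test. The point is minor, and worth making because the better model costs nothing.

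A reader might infer that the gate loses about 10 points of power for both co-primaries. The documents do not support that. The 9.7 points belong to the single SANDE test at an assumed 10-point interaction and an assumed |r| of 0.5. The documents give no interaction size, subgroup prevalence or baseline correlation. Protocol 9.1 bases SD 12 on variability in symptom scores and does not say these are change scores. If 12 is already the adjusted residual SD, the comparison at |r| = 0.5 is 53.3% against 62.4%. The defensible statement for SANDE is a gain of about 1 to 22 points over |r| from 0.2 to 0.7 for a 10-point interaction, and less if the interaction is smaller. The either-model gate and the Schirmer test gain less, as shown above. The case for including site is consistency with the primary model and the randomisation, not a power figure.

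**What to change.** In SAP 7.5, replace the three-term description with a statement that the interaction tests use the models of 10.1.2.1 and 10.1.2.2 (treatment, gender, age class, corresponding baseline value, site as random effect), fitted to the same imputed datasets, with the subgroup variable and the treatment-by-subgroup term added. This also brings the text into line with the ANCOVA titles and fixes the model before unblinding.

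The cost is one sentence and extra terms in eight models, with no new data. Region is constant within a site, but a random site intercept still allows a region term.
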